2. BACKGROUND INFORMATION AND SCIENTIFIC RATIONALE

2.1. Background Information

2.1.1. Introduction

Botulism is caused by absorption of Botulinum Neurotoxin (BoNT) into the blood stream following oral ingestion (food-borne botulism), through the growth of *C. botulinum* in the gastrointestinal tract (infant botulism), in wounds contaminated by the organism (wound botulism), or through inhalation (inhalation botulism).¹ There are 7 BoNT serotypes (A-G)² which differ by 35-68% at the amino acid level. Recent data has been published identifying a BoNT/H serotype that appears to be a hybrid of A and F serotype.³ Three of the BoNT serotypes (A, B, E) cause up to 99% of the cases of human botulism.^{4,5}

Botulism is characterized by prolonged paralysis, which is either immediately fatal or requires prolonged hospitalization in an Intensive Care Unit and mechanical ventilation. The onset and severity of symptoms depends on the amount of toxin absorbed. Onset of symptoms typically occurs 12-72 hours after ingestion, with a range of up to 8 days. Recovery from the paralysis does not occur until new nerve growth occurs. Mechanical ventilator support is commonly needed for 2 to 8 weeks, with some patients requiring support for up to 7 months.^{6,7}

The development of approaches to treat or prevent biothreat botulism has been designated a high priority area by the National Institute of Allergy and Infectious Diseases (NIAID) [see NIAID Biodefense Research Agenda for the Centers for Disease Control and Prevention (CDC) Category A Agents].⁸ In June 2011, the Federal Experts Advisory Panel (FESAP) published recommendations concerning the Select Agent Program to address the requirements of Executive Order 13546, “Optimizing the Security of Biological Select Agents and Toxins in the United States”, published in the Federal Register on July 8th, 2010; the recommendations of the FESAP classified Botulinum toxins as “Tier 1” agents.

2.1.2. Currently Available Treatments

Equine antitoxin and human botulism immune globulin are currently used to treat adult^{9,10} and infant botulism,¹¹ respectively. Traditional antitoxins are not readily renewable resources, requiring animal or human immunization, plasmapheresis or bleeding, and serum processing for each lot. Moreover, each lot produced will vary in antibody composition, potency, dosing, and possibly safety profile. Human botulism immune globulin is produced by plasmapheresing laboratory personnel who have been immunized because they are at risk of exposure to BoNT.¹¹ Although human botulism immune globulin has been shown to be both safe and effective for treating infant botulism, scaling of this product for the biothreat drug repository is not feasible.¹¹ Moreover, the pentavalent toxoid used to produce botulism immune globulin is no longer available,¹² raising questions concerning the ability to continue to make this product.

With the previous generation of equine antitoxin there was a 9% incidence of acute or delayed hypersensitivity reactions, including serum sickness (3.7%) and anaphylactic shock (1.9%).⁹ The observed side effects are attributable to the residual content of the equine Fc region. The current generation heptavalent equine antitoxin (HBAT) also is produced from horses, but is more

thoroughly digested to yield largely Fab and Fab'2 to theoretically reduce the incidence of hypersensitivity reactions.¹³ HBAT has a very short serum half-life (8-34 hours depending on serotype) and as a result, an approximately 2% incidence of recurrence of botulism occurs after treatment, a phenomenon called BoNT retoxication.¹⁴ HBAT has an approximately 1% incidence of anaphylaxis, as reported at the 2011 Interagency Botulism Coordinating Committee Meeting by CDC. Rapid deployment of equine antitoxin also is complicated by the inability to use it prophylactically and the need to dilute the product 10-fold and infuse intravenously (IV) slowly over hours. Finally, the potency of equine antitoxins, such as HBAT, can vary significantly for sub-serotypes where there is significant sequence difference between the immunizing sub-serotype and other sub-serotypes.

2.1.3. **G03-52-01 Development**

G03-52-01 drug product is being investigated for the treatment of botulinum neurotoxin and prophylaxis of inhalation botulism from serotypes A and B in adults. G03-52-01 is a mixture of five human IgG1 antibodies and one humanized IgG1 antibody each with distinct specificities that are individually expressed in a Chinese hamster ovary (CHO) cell line. Each of the drug substance antibodies (anti-BoNT/A NX01, NX02, NX11 and anti-BoNT/B XB10, XB18, XB23) used in the manufacture of G03-52-01 binds non-overlapping regions on BoNT/A or BoNT/B. While each of the mAbs binds to a distinct epitope on BoNT/A or BoNT/B, none was able to sufficiently neutralize BoNT when tested alone *in vivo*. The *in vivo* studies showed that the highest levels of mAb potency were dependent on the presence of three antibodies.¹⁵ The protective capacity of G03-52-01 to neutralize toxicity caused by BoNT/A and BoNT/B has been verified in mice and in guinea pigs.

As these drug products are directed at foreign targets not expressed in animals or humans and based on the observed lack of cross-reactivity of G03-52-01 in healthy human and animal tissue, the focus of the nonclinical safety evaluation of G03-52-01 was to assess potential off-target toxicity and to identify any untoward effects due to administration of either drug product.

A GLP 12-week repeat dose toxicity study was performed to evaluate the safety of G03-52-01 in rats when administered by intramuscular injection once weekly for three injections and to evaluate toxicity and reversibility of effects after a two-month recovery period. The study consisted of four Main Study/Recovery dose groups (15 rats/sex/group) and four Toxicokinetic (TK) dose groups (12 rats/sex/group). Experimental endpoints included moribundity/mortality; physical examinations, injection site (Draize) reactogenicity scoring; body weights; food consumption; body temperature measurements; clinical pathology parameters (clinical chemistry, hematology, and coagulation); serum drug levels/toxicokinetics; organ weights; gross pathology at necropsy; and microscopic pathology. IM treatment at doses of 10, 50, or 100 mg/kg of G03-52-01 against botulinum neurotoxins A and B did not result in any treatment-related, toxicologically significant, or adverse findings following three injections on Study Days 1, 8, and 15. Therefore, the No Observed Adverse Effect Level (NOAEL) was 100 mg/kg for this study.

2.1.4. Public Readiness and Emergency Preparedness Act

This protocol and the study product tested are covered under the Public Readiness and Emergency Preparedness (PREP) act. The PREP Act provides compensation to participants in the event of serious physical injury or death caused by covered drugs and vaccines, and liability protection for persons conducting the clinical trial and the manufacturer of the drug or vaccine.

On October 10, 2008, an amendment was issued to the Declaration for use of the PREP act to include countermeasures to treat, identify, or prevent adverse health consequences or death from exposure to botulinum toxin. (Federal Register, Volume 73, Number 202, Pages: 61864-61866). The study product used in this clinical trial is one such countermeasure. The PREP act provides immunity for covered persons (such as Manufacturers, Distributors, Program planners and other qualified persons who prescribe, administer or dispense the study product) from tort liability, unless the injury was caused by willful misconduct.

The PREP Act also authorized a “Covered Countermeasures Process Fund” to provide compensation to eligible individuals who suffer specified injuries from administration or use of a countermeasure pursuant to the declaration. Any requests for compensation must be filed within one year of administration or use of the countermeasure. Requests would go to the HRSA Preparedness Countermeasures Injury Compensation Program (<http://www.hrsa.gov/cicp>). Compensation may then be available for medical benefits, lost wages and death benefits to eligible individuals for specified injuries in accordance with regulations published by the Secretary. Eligibility for compensation and the injuries for which compensation may be available are further defined by regulation.

An individual who suffers a serious physical injury or death from the administration and use of the study product must first seek compensation from the Covered Countermeasures Process Fund. A serious physical injury means an injury that is life threatening, results in, or requires medical or surgical intervention to prevent, permanent impairment of a body function or permanent damage to body structure. Any compensation will be reduced by public or private insurance or worker’s compensation available to the injured individual.

If no funds have been appropriated to the compensation program, the Secretary does not make a final determination on the individual’s request within 240 days, or if the individual decides not to accept the compensation, the injured individual or his representative may pursue a tort claim in the US District Court for the District of Columbia, but only if the claim involves willful misconduct, is pled with particularity required under the PREP Act, verified, and accompanied by an affidavit by a physician who did not treat the individual and certified medical records. Any award is reduced by any public or private insurance or worker’s compensation available to the injured individual. Awards for non-economic damages, such as pain, suffering, physical impairment, mental anguish, and loss of consortium are also limited. If the individual accepts compensation, or if there is no willful misconduct, the individual does not have a tort claim that can be filed in a US Federal or a State court.

2.2. Rationale For Use of G03-52-01

Based on nonclinical and clinical experience with other anti-BoNT mAbs, use of G03-52-01 for the treatment of botulism and prophylaxis of inhalation botulism from serotypes A and B in adults may provide the following advantages over the equine antitoxins:

- An improved safety profile
 - Substantially decreased anaphylaxis and no risk of serum sickness
 - G03-52-01 is directed at foreign targets not expressed in animals or humans
 - Toxicity studies demonstrated a lack of cross-reactivity of G03-52-01 in healthy human tissue
 - A similar product targeting BoNT serotype A was well tolerated and no safety concerns were observed in a Phase 1 clinical study
 - A similar product targeting BoNT serotype B was well tolerated and no safety concerns were observed in a Phase 1 clinical trial
- A longer half-life
- The ability to administer repeated doses for prevention and therapy
- The ability to use small doses via IV and IM administration (permitting flexible administration scenarios, including self-administration)
- The ability to easily and consistently manufacture a large number of doses in sufficient quantities for stockpiling

The proposed starting dose for G03-52-01 dose escalation (10 mg IM) is based on previous toxicology and clinical studies of anti-BoNT mAbs that included intravenous dosing. The 10 mg IM dose includes 5 mg of anti-BoNT/A mAbs (NX01, NX02, and NX11; similar to NTM-1631, formerly XOMA 3AB) and 5 mg of anti-BoNT/B mAbs (XB10, XB18 and XB23; similar to NTM-1632, formerly XOMA 3B).

NTM-1631 and NTM-1632 have undergone Phase 1 clinical testing under protocols very similar to Protocol G03-52-001.001. These studies were placebo-controlled, double-blind, dose escalation studies to evaluate the safety and tolerability of each drug. Each subject received a single intravenous (IV) infusions of study drug or placebo administered over one hour, as an inpatient, at one of three dose levels (0.33, 0.165, or 0.033 mg/kg) equating to approximately 25, 12, or 2.5 mg assuming a 75 kg subject. All three doses of each drug were safe and generally well tolerated during and following infusion. No pattern of treatment emergent adverse events was seen at any of the doses. None of the three NTM-1631 mAbs induced an antibody response or augmentation of preexisting antibodies in the few subjects who had them and similar analysis of NTM-1632 antibody response is underway.

Doses will escalate to 25 mg and then to 50 mg up to 100mg provided there are no safety concerns. The nonclinical IND-enabling toxicology studies were designed to support this clinical design with intramuscular route of administration. Based on data received from the Day 60 blinded interim safety and PK analysis, it was determined to escalate to 100mg single dose.

2.3. Potential Risks and Benefits

2.3.1. Potential Risks

The potential risks to the subjects due to participation in the study are those related to venipuncture, the IM injection and the administration of G03-52-01

Venipuncture

Venipuncture causes transient discomfort and may cause fainting. Bruising at the site of the venipuncture may occur but can be prevented or lessened by applying pressure for several minutes. Infection at the site is possible but highly unlikely as aseptic technique must be employed.

IM Injection

An IM injection may cause some discomfort at the injection site. Other risks may include pain, redness, swelling, or warmth at the injection site. These risks are minimal.

G03-52-01

As G03-52-01 has not been administered to humans, the potential risks are based on adverse events associated with NTM-1631 and NTM-1632 in the Phase 1 studies, infusion or injection of other antibody products, in particular other monoclonal antibody preparations against non-human targets, and the possibility of allergic reactions, especially IgE-mediated and serum sickness-like reactions.

Adverse Events with a Similar Product

A summary of all Adverse Events (AEs) assessed as related on the NTM-1631 clinical protocol following administration of NTM-1631 follows:

NTM-1631 dose level 0.033mg/kg:

- One female subject experienced a moderate decrease in hemoglobin reported 1-week post infusion. She also had a mild elevation in Alanine Aminotransferase (ALT) 2 weeks post infusion.
- One male subject experienced moderate protein in the urine one-week post infusion and a mild elevation in Aspartate Aminotransferase (AST) two months post infusion.
- One male subject experienced a moderate elevation in blood sugar three days post infusion and then again two weeks post infusion.

NTM-1631 dose level 0.165mg/kg:

- One female subject experienced a mild increase in neutrophils starting one-month post infusion.

NTM-1631 dose level 0.330mg/kg:

- No associated AEs were reported in subjects receiving NTM-1631 at this dose.

No safety signals or trends were identified on this protocol and a placebo subject also had a mild increase in AST and ALT three days post infusion.

A summary of all AEs assessed as related with the NTM-1632 clinical protocol following administration of NTM-1632 is as follows:

NTM-1632 dose level 0.033mg/kg:

- One female subject experienced mild throbbing pressure on forehead during infusion
- One female subject experienced mild lightheadedness during infusion

NTM-1632 dose level 0.33mg/kg

- One female subject experienced mild loose stools 1-day post infusion

Risk Factors Associated with Monoclonal Antibodies

Injections of mAbs may be associated with injection reactions including: anaphylaxis/anaphylactoid type reaction, especially during a first exposure, and when administered rapidly. Fever, chills and rigors, typically occurring within the first two hours following injection, characterize these reactions. Other symptoms sometimes associated with injection reactions include nausea, vomiting, rash, pruritus, bronchospasm or other acute pulmonary response, angioedema, hypotension, hypertension, cardiac arrhythmias, dizziness, dyspnea, headache, and malaise.

Risk of Immunogenicity

Antibodies directed against G03-52-01 may develop following injection. This will be assessed by taking blood samples at selected visits throughout the study. G03-52-01 is a fully humanized mAb which based on experience with other humanized or chimeric mAbs, reduces the immunogenic potential.

2.3.2. Known Potential Benefits

This trial has no benefit for the subjects participating in the trial. The knowledge gained in this trial may help society, especially those exposed to, or at risk of being exposed to, the toxins of botulism.

3. OBJECTIVES**3.1. Study Objectives**

Primary Objective:

- To assess the safety and tolerability of escalating doses of G03-52-01 administered IM in healthy adult subjects.

Secondary Objective:

- To assess the (PK) and immunogenicity of escalating doses of G03-52-01 administered IM in healthy adult subjects.

3.2. Study Outcome Measures

3.2.1. Primary Endpoints

- The occurrence of Serious Adverse Events following administration of G03-52-01 to the final follow-up visit.
- The occurrence of Adverse Events from administration of G03-52-01 to the final follow-up visit.
- The occurrence of changes from baseline in physical examination, vital signs and clinical safety laboratory values following administration of G03-52-01 to the final follow-up visit.

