	
 • Samples collected to evaluate presence of anti-drug antibodies (ADA) collected for all cohorts. 
 ○ Samples will be tested for ADA at pre-dose and on Days 15, 30, 45, 60, 90, and 120 for Cohorts 1-3. ○ Samples will be tested for ADA at pre-dose and on Days 45, 60, 90, 120, and 180 for Cohort 4.
Estimated Time to Complete Enrollment:	Approximately 5 months.
Description of Study Design:	
A Phase 1, randomized, double-blind, placebo-controlled dose escalation trial of four dose cohorts outlined below:
 
 • Cohort 1: 10 mg IM injection (8 active, 2 placebo) • Cohort 2: 25 mg IM injection (8 active, 2 placebo) • Cohort 3: 50 mg IM injection (8 active, 2 placebo) • Cohort 4: 100mg IM injection (8 active, 2 placebo) 
Dosing for each cohort is as follows: Two sentinel subjects will be administered a single IM dose (one G03-52-01, one placebo). The dosing of the remaining eight subjects within that cohort will not be initiated until at least 24 hours have passed and no adverse events have occurred that meet halting criteria, and no safety signals have occurred that in the opinion of the investigator warrant further investigation. The remaining eight subjects in the cohort will be admitted as scheduled without delay. Dose escalation will not occur until safety data through Day 8 is reviewed by the Safety Review Committee (SRC) composed of the Principal Investigator (PI), Ology Bioservices Medical Monitor, and the ICON Medical Monitor. Objective dose-escalation criteria and safety evaluations will be utilized. A SRC meeting will be held at any time during the course of the study if halting criteria are met or safety concerns arise.
 
The study will consist of a twenty-eight-day screening period and up to 12-hour clinic stay. Follow-up visits will occur at 24 hours, 48 hours, and 72 hours post dose and on Days 4, 8, 15, 30, 45, 60, 90, and 120 for Cohorts 1-3. Follow-up visits for subjects in Cohort 4 will occur at on Days 1, 2, 4, 8, 15, 30, 45, 60, 90, 120, and 180.
 
Subjects will be screened for Human Immunodeficiency Virus (HIV), Hepatitis B surface antigen (HBsAg), and antibody to Hepatitis C virus (HCV), drugs and alcohol. Safety parameters include physical examination, 12-lead Electrocardiogram (ECG), vital signs, and clinical laboratory values to include:

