4. STUDY DESIGN

This is a Phase 1, single-center, placebo-controlled, double-blind, dose-escalation study to evaluate the safety and tolerability of G03-52-01 in healthy adults. This is a first-in-human study consisting of four Cohorts of ten subjects each. Each subject will receive a single IM injection of G03-52-01 or placebo.

Table 1: Cohorts

Cohort	Dose of G03-52-01	Number of Subjects
1	10 mg	10 subjects (8 active, 2 placebo)
2	25 mg	10 subjects (8 active, 2 placebo)
3	50 mg	10 subjects (8 active, 2 placebo)
4	100 mg	10 subjects (8 active, 2 placebo)

Schedule for Subjects

Subjects in Cohorts 1-3 will participate in the study for approximately 150 days, including a 28-day screening period, up to 12-hour inpatient stay and approximately 120-day follow-up after study product administration. Subjects will remain at the clinic and not be eligible for discharge until 8 hours after the IM injection. Last follow up visit scheduled at Day 120.

Subjects in Cohort 4 will participate in the study for approximately 210 days, including a 28-day screening period, up to a 12-hour clinic stay and approximately 180-day follow-up after study product administration. Subjects will remain at the clinic and not be eligible for discharge until approximately 8 hours after the IM injection. Last follow up visit scheduled at Day 180.

The end of the study is defined as the date of the last visit of the last subject in the study.

Schedule for Cohorts

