6.3. Vital Signs

Vital sign assessments including systolic and diastolic blood pressure (BP) [measured after sitting for at least 10 minutes], heart rate (HR), and oral temperature will be performed at each in-clinic study visit. Vital signs that are thought to be aberrant due to an error in measurement may be repeated. During screening and follow-up, a measurement that is a Grade 1 (as referenced in Appendix B Toxicity Grading) may be repeated once if the PI believes a transient condition led to the aberrant value.

Vital signs obtained at screening will serve as baseline values for the subject. Grade 1 values are allowable unless deemed clinically significant by the study investigator.

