7.5. Visit 5: Out-patient Follow-up (72 hours) Cohorts 1-3

- Obtain vital signs
- Review and update concomitant medications
- Perform symptom directed PE
- Obtain blood samples for the following:
 - PK measurement at 72 hours (+/- 2 hours)
- Counsel women of child-bearing potential on the avoidance of pregnancy
- Counsel the subject not to receive any botulinum toxin preparation (e.g., Botox) for 4 months after injection.
- Assessment of AEs and SAEs

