7.12. Visit 12: Out-patient Follow-up (Day 90±3)

- Obtain vital signs
- Review and update concomitant medications
- Perform symptom directed PE
- Obtain blood samples for the following:
 - PK measurement
 - MNA
 - ADA
- Assessment of AEs and SAEs
- Counsel women of child-bearing potential on the avoidance of pregnancy
- Counsel the subject not to receive any botulinum toxin preparation (e.g. Botox) for 4 months after injection
- Assessment of COVID-19 vaccination status.

7.13. Visit 13: Final Visit / Early Termination Visit for Cohorts 1-3 (Day 120±3) / Cohort 4 (Day 120±3)

- Obtain vital signs
- Review and update concomitant medications
- Perform symptom directed PE
- Obtain blood samples for the following:
 - Clinical Safety labs (Cohorts 1-3 Only)
 - PK measurement
 - MNA
 - ADA
- Obtain urine sample for dipstick analysis
- Perform urine pregnancy test on women of child-bearing potential
- Assessment of AEs and SAEs
- Counsel women of child-bearing potential on the avoidance of pregnancy
- Counsel the subject not to receive any botulinum toxin preparation (e.g. Botox) for 4 months after injection
- Assessment of COVID-19 vaccination status.

**7.14. Visit 14: Final Visit/ Early Termination for Subjects in Cohort 4
(Day 180±3)**

- Obtain vital signs
- Review and update concomitant medications
- Perform symptom directed PE
- Obtain blood samples for the following:
 - Clinical Safety Labs
 - PK measurement
 - ADA
- Obtain urine sample for dipstick analysis
- Perform urine pregnancy test on women of child-bearing potential
- Assessment of AEs and SAEs
- Counsel women of child-bearing potential on the avoidance of pregnancy
- Counsel the subject not to receive any botulinum toxin preparation (e.g. Botox) for 4 months after injection
- Assessment of COVID-19 vaccination status.

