APPENDIX B: TOXICITY GRADING

Clinical Adverse Events			
VITAL SIGNS	Mild (Grade 1)	Moderate (Grade 2)	Severe Grade 3
Fever - °C	38.0-38.4	38.5-38.9	>38.9
Tachycardia - bpm	101-115	116-130	>130 or ventricular dysrhythmias
Bradycardia – bpm • Baseline \geq 60 OR, if Baseline $<$ 60 Baseline $<$ 60	• 50-54 OR, if Baseline $<$ 60, • 45-50	• 45-49 OR, if baseline $<$ 60, • 40-44	• <45 OR, if baseline $<$ 60 • <40
Hypertension (systolic) - mmHg	141-150	151-160	>160
Hypertension (diastolic) - mmHg	91-95	96-100	>100
Hypotension (systolic) - mmHg	85-89	80-84	<80
Tachypnea – breaths per min	23-25	26-30	>30
CARDIOVASCULAR	Mild (Grade 1)	Moderate (Grade 2)	Severe (Grade 3)
Arrhythmia		Asymptomatic; transient signs; no medical intervention required	Recurrent/persistent; symptomatic medical intervention required
Hemorrhage, Blood Loss	Estimated blood loss \leq 100 mL	Estimated blood loss >100 mL; no transfusion required	Transfusion required
QTc (Fridericia's correction) ¹	Asymptomatic, QTc interval 450-479 msec	Asymptomatic; QTc interval 480 to 499 msec OR Increase in interval 30-59 msec above baseline	Asymptomatic; QTc interval \geq 500 msec OR Increase in interval \geq 60 msec above baseline
PR Interval (prolonged) ¹	PR interval 0.21-0.25 sec	PR interval >0.25	Type II 2 nd degree AV block OR Ventricular pause >3.0 sec
RESPIRATORY	Mild (Grade 1)	Moderate (Grade 2)	Severe (Grade 3)
Cough	Transient; no treatment	Persistent cough	Interferes with daily activities
Bronchospasm, Acute	Transient; no treatment; FEV1 71-80% of predicted peak flow	Requires medical intervention; normalizes with bronchodilator; FEV1 60-70% of predicted peak flow	No normalization with bronchodilator; FEV1 <60% of predicted peak flow
Dyspnea	Does not interfere with usual and social activities	Interferes with usual and social activities; no treatment	Prevents daily and usual social activity OR requires treatment
GASTROINTESTINAL	Mild (Grade 1)	Moderate (Grade 2)	Severe (Grade 3)

¹Inclusion dependent upon protocol requirements.

Nausea	No interference with activity	Some interference with activity	Prevents daily activities
Vomiting	No interference with activity OR 1-2 episodes/24 hours	Some interference with activity OR >2 episodes/24 hours	Prevents daily activity OR requires IV hydration OR requires medical intervention

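### The AE and SAE tables set 180 days of follow-up at 100 mg beside 120 days at the lower doses with no common window, so any background events in Days 121-180 would raise the 100 mg column without a drug effect

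*Protocol*

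**What the plan says.** Protocol 3.2.1 and SAP 2.2.1 define the AE endpoint as "The occurrence of Adverse Events from administration of G03-52-01 to the final follow-up visit"; the SAE endpoint has the same end. Under Protocol 8.3.2, SAEs are collected to each subject's last visit. After the study, only SAEs suspected to be related, and that the investigator learns of, are reported.

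Protocol 4 fixes the end of follow-up by cohort. For Cohorts 1-3 it is "Last follow up visit scheduled at Day 120"; for Cohort 4 it is "Last follow up visit scheduled at Day 180". The visit schedules also differ: "Follow-up visits for subjects in Cohort 4 will occur at on Days 1, 2, 4, 8, 15, 30, 45, 60, 90, 120, and 180" (Protocol Summary), while the 72-hour visit belongs to the other cohorts ("Visit 5: Out-patient Follow-up (72 hours) Cohorts 1-3").

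Each cohort has 8 active and 2 placebo subjects. SAP 7.1 and 7.22 pool placebo across cohorts. SAP 7.22.1 counts every AE that begins or worsens after dosing and reports subjects (%) and events by dose cohort and control group. It sets a start but no end day, and it uses no person-time. The titles of Tables 14.3.1.1 to 14.3.1.4 carry no cut-off. The SAP 2.0 revision history, which brought in Cohort 4, lists only a MedDRA version change for 7.22.1.

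**The concern.** The primary objective is the safety and tolerability of escalating doses, so these tables are there to be read across the dose columns. The top dose is also the only dose followed for 180 days. An unrelated illness starting on Day 150 would count at 100 mg, but would normally never be collected at 10, 25 or 50 mg. Pooled placebo does not correct this, because 6 of its 8 subjects also stop at Day 120 and 100 mg is never tabulated against its own 180-day controls. A reader could take the result for a dose trend.

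**Working it through.** The plan gives no background AE rate and no exposure-adjusted figure, so there is no figure of its own to reproduce on this point. The only event rates in the documents are the 0.15 to 0.5 in Protocol 10.1. They are used below as assumed Day-120 incidences. (That section's probabilities of 0.728 to 0.996 equal 1 − (1 − p)^8, so they are for eight subjects; ten give 0.803 to 0.999. This does not bear on the present point.)

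**1. Planned person-days**
- 100 mg: 8 × 180 = 1440
- Each lower dose: 8 × 120 = 960
- Pooled placebo: 6 × 120 + 2 × 180 = 1080, a mean of 135 per subject

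**2. Event counts.** Let r be the background event rate in Days 121-180 relative to Days 0-120, assumed to lie between 0 and 1, with no drug effect and no dropout. The ratio against a lower dose is 1 + 0.5r, so 1.0 to 1.5. At r = 1 the ±3-day visit windows move it between 177/123 = 1.44 and 183/117 = 1.56. Against placebo the ratio is (1 + 0.5r)/(1 + 0.125r), so 1.0 to 1.33.

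**3. Affected subjects.** With the same risk in every subject, p180 = 1 − (1 − p120)^(1 + 0.5r). Pooled placebo is (6·p120 + 2·p180)/8. Expected subjects out of 8, and the probability that 100 mg shows strictly more (or fewer) affected subjects than one given lower dose:

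| p120 | r | Lower dose | Placebo | 100 mg | Excess over lower dose, points | P(more) / P(fewer) |
|---|---|---|---|---|---|---|
| 15% | 0 | 1.20 | 1.20 | 1.20 | 0 | 0.357 / 0.357 |
| 15% | 0.5 | 1.20 | 1.27 | 1.47 | +3.4 | 0.435 / 0.297 |
| 15% | 1 | 1.20 | 1.33 | 1.73 | +6.6 | 0.506 / 0.247 |
| 30% | 0 | 2.40 | 2.40 | 2.40 | 0 | 0.392 / 0.392 |
| 30% | 0.5 | 2.40 | 2.52 | 2.88 | +6.0 | 0.497 / 0.300 |
| 30% | 1 | 2.40 | 2.63 | 3.31 | +11.4 | 0.589 / 0.227 |
| 50% | 0 | 4.00 | 4.00 | 4.00 | 0 | 0.402 / 0.402 |
| 50% | 0.5 | 4.00 | 4.16 | 4.64 | +8.0 | 0.530 / 0.283 |
| 50% | 1 | 4.00 | 4.29 | 5.17 | +14.6 | 0.638 / 0.196 |

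The excess over placebo is 0.75 times the excess over a lower dose, so at most +5.0 (15%) to +11.0 (50%). If risk varies between subjects (gamma frailty, variance 1), p180 = 1 − 1/(1 + H(1 + 0.5r)) with H = 1/(1 − p120) − 1. At 50% this gives +10.0 for r = 1 and +5.6 for r = 0.5.

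**4. SAEs.** The extra observation at 100 mg is 8 × 60/365.25 = 1.31 person-years. At an assumed 0.5 to 5 SAEs per 100 person-years, the excess is 0.007 to 0.066 SAE.

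**5. Noise.** At 50% incidence the SD of the difference between two groups of 8 is √(8 × 0.25 + 8 × 0.25) = 2.0 subjects. The largest shift in the table is 8 × 0.146 = 1.17 subjects.

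**6. Findings made only at scheduled measurements**
- Vital signs: "oral temperature will be performed at each in-clinic study visit" (Protocol 6.3), and Appendix B grades them under "Clinical Adverse Events". Both schedules have 11 post-dose visits, since Cohort 4 drops 72 h and adds Day 180.
- Blood safety labs: Protocol 7.13 limits the Day 120 draw, "Clinical Safety labs (Cohorts 1-3 Only"). By Table 2 and the visit lists each schedule has 4 post-dose draws (Days 8, 15, 30, then 120 or 180). Protocol 6.5.2 and SAP 3.16 mention only screening and end of study, which would give one post-dose draw each, still equal.
- Urine dipstick: Protocol 7.13 does not restrict it at Day 120 and 7.14 repeats it at Day 180, so Cohort 4 has two after dosing against one. Footnote 18 of Appendix A limits the Day 120 dipstick to Cohorts 1-3, which gives one each. The passages conflict.

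**7. With a Day-120 cut.** Every column has 8 × 120 = 960 planned person-days, and the expected ratio is 1.00 for any background rate.

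**The case against.** The strongest case against is that little harm follows. The comparison is descriptive, and with 8 per group 100 mg would exceed a given lower dose 36% to 40% of the time even with equal windows. Dated AE listings let a careful reader pick out late events. Table 14.3.1.4 splits AEs by relationship, and many late illnesses would probably be judged unrelated. SAEs are also reviewed and listed individually. All of this stands and limits the importance.

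Recall limits the size too. No visit falls between Day 120 and Day 180, so that window rests on one visit and a 60-day recall. Reported late events would probably run below a constant rate, which makes r = 1 an upper case.

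Two arguments do not remove the mismatch. SAP 7.23 speaks of an interim through Day 120, but it is blinded, concerns Cohorts 1-3 and lists no AE table by dose; the Cohort 4 interim stops at Day 90. SAP 3.15 monitors AEs to end of study, which Protocol 4 defines by the last subject's last visit. Cohorts 1-3 nevertheless have no scheduled visit after Day 120, and their endpoint stops there.

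A reader might also infer that every kind of AE is inflated because Cohort 4 is measured for longer. The schedules do not support that for vital signs or blood labs, where the number of post-dose measurements is equal. For urine findings the question stays open until the dipstick passages are reconciled.

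**Conclusion.** The point holds as a conditional statement about expectation: any background symptom or illness AEs, or SAEs, that begin in Days 121-180 add to the 100 mg column and cannot add to the lower-dose columns. The mismatch itself is certain from the text. Its size is not, since it rests on an assumed background rate, an assumed r between 0 and 1, no drug effect and full retention. The excess in affected subjects lies between 0 and +6.6 (15% incidence) or +14.6 (50%) points over lower doses. For SAEs it is well under 0.1 event.

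A reader might infer that the tables will show a false dose trend of about 15 points, or a false-positive finding. The documents support neither. The first figure takes both the top of the assumed incidence range and a constant late rate, and no between-dose test is planned. Nor is dose escalation compromised: it rests on Day 8 reviews and, for 100 mg, on the Day 60 blinded interim (Protocol 2.2). The by-visit laboratory and vital-sign tables are unaffected. The change should be made because the bias sits in the primary safety display, at the top dose, and is cheap to remove.

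**What to change.** Keep the tables that run to the final visit, and add the following to SAP 7.22.1 and the table list before unblinding.

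- Day-120 versions of Tables 14.3.1.1 to 14.3.1.4, limited to TEAEs and SAEs with onset through the subject's Day 120 visit. If that visit is missing, cut at SAP relative day 121 (protocol Day 120, because the SAP adds 1), or at last contact if earlier. Name these tables as the basis for reading across doses and against placebo.
- One adjacent table of later Cohort 4 events (8 active, 2 placebo), so that no safety information is lost.
- A rule for partial onset dates in Cohort 4. SAP 7.2.1 moves them to the first of the month or 1 January, no earlier than the dose date, which could pull late events into the Day-120 tables. The imputed date alone should not decide: assign these events by the visit at which they were first reported (after the Day 120 visit means late), and flag them.
- A footnote that by Day 120 Cohort 4 has one fewer blood safety-lab draw (3 against 4) and one fewer vital-sign visit (10 against 11). State the dipstick count once Protocol 7.13, 7.14 and Appendix A footnote 18 agree.

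The cost is SAP wording, up to five extra tables and a small assignment rule. Onset dates are already collected and relative onset day is already derived. The AE fields listed in Protocol 8.3.1 and SAP 3.15 do not include the reporting visit, so for the few partial dates it may have to come from source records. No endpoint changes.
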